		
Justification: We are aiming to include participants who can benefit from the treatment to reduce postoperative pain at home and have seen that there is a time lag in pain which potentially increases after discharge. Therefore, we are amending the final inclusion criteria from Postop pain VAS <math>\geq 5</math> in PACU, where analgesia can still be in effect, to VAS <math>>0</math> postop which will better capture the population of interest.
 
2) Revising the subject demographics questionnaire Justification: We have added 'Procedure to be Performed, Physician performing procedure, Tissue to be Operated On and Additional procedure details (such as splints, etc.)' to the demographic form to capture additional information that will allow us to segment results of the primary endpoint of acute change in peak postoperative pain
 
3) Updated Post-op timelines day 7 and day 14 to allow follow-up up to 21 post-surgeries to accommodate change in patient and clinic scheduling that occur for varying reasons
 
4) Updated Study Population to expand scope to include patients electing for functional nasal surgery, common among patients requiring functional rhinoplasty or reconstructive surgery
 
5) Rephrasing Compensation language

V1.1	1.17.2024	
Increased recruitment numbers from 100 to 130. Justification: due to high drop-out rate post randomization; there is the need to increase the recruitment numbers to reach the target of 60 completed participants.

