On the day of surgery, standard total intravenous anesthesia (TIVA) will be administered for each enrolled subject. Standard TIVA is as follows: anesthetic induction will be performed using propofol 1.5-2.5 mg/kg and remifentanil 2-5 mcg/kg, with neuromuscular blockade used to facilitate endotracheal intubation only if deemed necessary by the anesthesiologist placing the endotracheal tube (ETT). Anesthesia will be maintained using propofol 30-50 mcg/kg/min, remifentanil 0.05-0.5 mcg/kg/min and nitrous oxide 50-70% titrated based on hemodynamics to maintain a mean arterial pressure of 60-70 mmHg. Each subject will receive the standard dose of 10 mg intravenous dexamethasone prior to the start of surgery, and 4 mg ondansetron prior to emergence. Vital signs, anesthetic technique (i.e., bolus and infusion drug totals, end tidal gas concentrations, narrative comments), and inputs and outputs for the case will be recorded to control hemodynamic differences between subjects. No new imaging will be obtained as part of the study. In PACU phase II, subjects will report their visual analog scale (VAS) for pain to confirm eligibility for the study. Subjects will complete their first study device treatment in the PACU phase II and study staff will record their VAS for pain before treatment and 10 minutes and 1 hour after treatment. Subjects will be instructed to record their VAS for pain at 2 hours and 4 hours after treatment at home.

The day after surgery, subjects will be reminded by staff members via phone to self-administer the treatment with the device. Subjects will glide the device over the periorbital skin for 2.5 minutes per side of the face (five minutes total) three times every 24 hours for up to V2 or 21 days post-op, whichever comes sooner with additional administrations as needed. When in pain, subjects will be instructed to use the device and wait ten minutes before using oxycodone 5 mg or acetaminophen 325 mg as rescue pain medication if needed. Subjects will complete a daily pain diary (either paper or online via REDCap) documenting their pain on a visual analog scale of 0-10 before and 10 minutes, 1 hour, 2 hour, 4 hours after treatment. Subjects will also record the time and dose of all medications used (either paper or online via REDCap). The questions asked are as follows:

- How many times did you administer the device today?
- How many acetaminophen 325 mg have you taken in the last 24 hours?

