- How many oxycodone 5 mg have you taken in the last 24 hours?

- Were you able to complete your daily work activities?
- Were you able to complete your daily non-work activities?

Subjects will return to clinic for their first two postoperative visits o . On postoperative V1 and V2 subjects will complete a modified version of the NOSE questionnaire to quantify changes in congestion and nasal obstruction. Post-op V2 subjects will complete the SNOT-22 to capture other sinonasal symptoms. For patients undergoing debridement, upon arriving in clinic, subjects will be instructed to record their current pain level via VAS in their pain diary before and after they self-administer treatment with the study device. They will subsequently record their pain levels during and after the debridement. During the second postop visit, subjects will be asked to complete a user experience questionnaire assessing their satisfaction with the study device and safety/tolerability.

- **Data analysis**

All data will be tabulated. The difference between the symptom scores before and after treatment will be computed for each individual in the study. Differences in change scores will be compared across treatment groups.

An appropriate two-sided statistical test (paired t-test or repeated measure ANOVA) will be used to assess the pre and post differences in symptom severity.

- **STUDY ENDPOINTS**

This study is intended to assess the analgesic efficacy and safety of the study device after functional nasal or sinus surgery. The primary endpoint is the acute change in peak postoperative pain score 10 minutes after treatment.

Auxiliary outcomes include:

- Pain at 1 hour, 2 hours, 4 hours after device treatment
- Pain before, during, and after debridement (applicable to FESS patients)
- Postoperative debridement compliance (applicable to FESS patients)
- Self-report of congestion and nasal obstruction severity
- Total opioid and/or acetaminophen consumption (the former calculated in oral morphine equivalents)
- Patient satisfaction
- Safety and tolerability
- Direct and indirect cost of pain management as calculated by total medications used and number of days missed from usual daily activity
- Utilization of additional healthcare resources (including telephone encounters and visits to any healthcare provider regarding postoperative pain)

- **INDUSTRY COLLABORATOR AND INVESTIGATOR OBLIGATIONS**

- **IRB Review/Approval/Reporting**

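### The tests named for pain leave the primary contrast unadjusted for pre-treatment pain, and a classical ANOVA over the later scores would drop any subject with one blank

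*Combined protocol and SAP*

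**What the plan says.** The whole analysis plan is the short Data analysis section under Study Procedures. It computes a before-after difference for each individual and then states: "Differences in change scores will be compared across treatment groups". No test is named for that step. The next sentence says "An appropriate two-sided statistical test (paired t-test or repeated measure ANOVA) will be used" to judge how symptom scores change from before to after treatment. The section does not say which test serves which endpoint, which time points would enter an ANOVA, whether a sphericity correction applies, or how missing scores are handled. The rule on blank fields under Data Retention concerns form completion only.

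Under Study Endpoints, "The primary endpoint is the acute change in peak postoperative pain score 10 minutes after treatment". The first auxiliary outcome is "Pain at 1 hour, 2 hours, 4 hours after device treatment".

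The Study procedure section has pain scored "before and 10 minutes, 1 hour, 2 hour, 4 hours after treatment", with treatments "three times every 24 hours for up to V2 or 21 days post-op, whichever comes sooner with additional administrations as needed". In the PACU session, staff record the before, 10-minute and 1-hour scores, and the subject records the 2- and 4-hour scores at home. The at-home list in the study flow leaves out the 1-hour score.

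The amendment log (V1.1) raises recruitment to 130 "due to high drop-out rate post randomization".

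**The concern.** Of the two named tests, only repeated-measures ANOVA can compare arms over time, so it is the natural candidate for the 1, 2 and 4 hour outcomes. In its classical form it needs a complete set of scores from every subject, and it assumes sphericity, which scores taken at unequal intervals over four hours are unlikely to meet. These scores are partly self-recorded at home in a trial that reports high drop-out. At stake are subjects discarded for one blank entry and an arm-by-time test that rejects too often.

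For the primary endpoint the issue is different. A two-score ANOVA is a change-score comparison and makes no use of the pre-treatment score as a covariate. A paired t-test only asks whether pain fell within an arm, which does not answer the trial's question.

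**Working it through.** The documents give no alpha, power, effect size, SD or missing rate, so the target of 60 cannot be reproduced. The missing rates and correlations below are assumptions.

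**1. Primary endpoint: two scores.** With k = 2 levels there is a single within-subject contrast, so epsilon = 1 exactly. The group-by-time F equals the square of the two-sample t on change scores. In one simulated data set (30 per arm) both were 0.6774, with p = 0.414. Simulated type I error over 10,000 runs was 4.7-5.0%. Anyone missing either score has no observed change, so the ANOVA drops nobody whom the change-score test keeps.

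**2. Primary endpoint: what adjustment adds.** Assume equal SD (σ) before and after, and correlation ρ between the two scores. The change score has variance 2σ²(1 − ρ). The ANCOVA residual variance is σ²(1 − ρ²). The ratio is (1 + ρ)/2, apart from one degree of freedom:
- ρ = 0.5: 1.5/2 = 0.75
- ρ = 0.7: 1.7/2 = 0.85
- ρ = 0.9: 1.9/2 = 0.95

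The variance of the arm contrast therefore falls by 25%, 15% or 5%.

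**3. Auxiliary series: subjects kept.** Let each score be missing independently with probability m. A five-score ANOVA (before, 10 min, 1, 2, 4 h) keeps 60(1 − m)^5 subjects. A contrast at one time that needs only the before score and that time's score has 60(1 − m)^2. The SE ratio is the square root of the second count over the first.

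| m | all five scores | before + one time | SE ratio |
|---|---|---|---|
| 2% | 54.2 | 57.6 | 1.03 |
| 5% | 46.4 | 54.1 | 1.08 |
| 10% | 35.4 | 48.6 | 1.17 |
| 20% | 19.7 | 38.4 | 1.40 |

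**4. Auxiliary series: sphericity.** Arm-by-time F over five levels, 30 per arm, no true effect, 10,000 runs (Monte Carlo SE at 5% = √(0.05 × 0.95/10,000) = 0.22 percentage points):

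| assumed correlation | epsilon | uncorrected type I error |
|---|---|---|
| AR(1) 0.5 | 0.81 | 6.3% |
| AR(1) 0.7 | 0.69 | 7.0% |
| AR(1) 0.9 | 0.58 | 7.9% |
| compound symmetry | 1.00 | 5.1% |

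With the Greenhouse-Geisser correction, the three AR(1) settings give 4.6-4.9%.

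**The case against.** The strongest reply is that the plan does not specify a five-score ANOVA. It offers two tests, ties neither to an endpoint, and computes a change for each individual first, so a blank 4-hour score need not remove a 10-minute change. This stands. A reader might infer that blank later scores would cut the power of the primary comparison. At an assumed effect of 0.74 SD, for example, five-score deletion gives 71% and 60% power at 5% and 10% missing, against 78% and 73% with the two needed scores. The documents do not support that inference, because the primary endpoint uses two scores only. For the auxiliary outcomes, the loss is a risk of an open plan and not a stated consequence.

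A reader might also infer that no between-arm comparison is planned. One is planned, since change scores are to be compared across groups. What is missing is a named test for it.

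Silence about a correction does not mean none would be used. The inflation is modest, and a Greenhouse-Geisser correction removes it. That correction does not bring back deleted subjects.

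Finally, the reported drop-out is not evidence of blanks within a session. Recruiting 130 to reach 60 implies a combined loss of 1 − 60/130 = 53.8%, but the Subject Population section attributes this to drop-outs and/or screen failures without a split. Devices are assigned before surgery and eligibility is confirmed afterwards in PACU, so some of those lost may have no treatment scores. No model recovers them.

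**Conclusion.** The point holds as a weakness that should be corrected before unblinding. For the primary endpoint, the named ANOVA is valid and costs no subjects, but it forgoes adjustment for a score already collected. That adjustment is worth 5-25% of the variance at assumed correlations of 0.9 down to 0.5. The other named test, the paired t-test, does not compare active with sham. For the auxiliary 1, 2 and 4 hour scores, a classical ANOVA over the series would keep about 46 or 35 of 60 subjects at an assumed 5% or 10% missing per score. If uncorrected, it would run at about 6-8% type I error under assumed AR(1) correlation. These sizes rest on assumed rates, independent missingness and assumed correlations. Only the two-score result (epsilon of 1, and F equal to t squared) is exact.

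**What to change.** In Data analysis, replace the two named tests as follows.

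1. **Primary endpoint.** Compare arms on the 10-minute score (or change) in the peak-pain session by two-sided ANCOVA, adjusting for that session's pre-treatment score and using everyone with both scores. State how the session is identified, which the plan does not do.
2. **Auxiliary 1, 2 and 4 hour pain.** Fit a likelihood-based mixed model for repeated measures to the post-treatment scores of the same session, with arm, time, arm-by-time and pre-treatment score, unstructured covariance and all observed scores. Read the arm contrast at each time.
3. **No pooling in the primary contrast.** Do not combine sessions or days there, because that would change the peak-pain endpoint.

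Reconcile the two lists of home scores as well, so that the status of the 1-hour score is clear.

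The cost is one paragraph, slightly more analysis work and no new data. The mixed model relies on scores being missing at random and still needs the pre-treatment score. If the peak session is not the first, that score follows earlier device use, so the adjusted contrast describes the acute response given pain at that moment.
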